Aim 1. Measure impact of apps on access to dermatology care. *San Francisco VA Health Care System's involvement is limited in Aim 1. All data related to this aim is collected by the VA's Center for Access Policy, Evaluation Research (CAPER) located at the Boston VA Health Care System. All data collected from the Corporate Data Warehouse, or any other databases as approved by the Boston VA Health Care System IRB will be anonymously recorded, aggregated, and shared with investigators and study staff at the San Francisco VA Health Care System and other sites. No analysis of the primary data will occur at San Francisco VA.*

Both apps will be made available over a 2 year period in a randomized, stepped-wedge design to Veterans Health Administration (VHA) facilities, after each app becomes available. The *VA Telederm* app will be distributed to 36 eligible VHA facilities that currently have low teledermatology activity and thus have had relatively poor adoption of basic consultative teledermatology. The *My Telederm* app will be distributed to 24 facilities with dermatology clinics that currently have relatively high teledermatology activity and thus already have relatively mature teledermatology programs ready for advanced operations.

By using health factors and stop codes unique to each app, we will use the VA Corporate Data Warehouse (CDW) to measure the impact of both apps on the following outcomes reflecting dermatology access: 1) Consult and appointment completion times for both teledermatology and in-person consults, stratified by new and established patients (primary outcome); 2) Instances of

dermatologic care (associated with either teledermatology or in-person dermatology encounters); and 3) Travel costs for VA, as well as non-VA care consult rates and associated costs. In addition, the following outcomes will be measured specifically for the *My Telederm* app: 1) Proportions of new patient encounters in-person dermatology clinics; and 2) “No-show” rates and timeliness of follow-up. Results of each of these access measures will be stratified to examine the effect on rural/highly rural Veterans, as well as to determine whether a differential effect occurs for facilities with some pre-existing teledermatology relative to those that had none.

Aim 2. Determine the factors that affect personal and organizational adoption of mobile apps.

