Using the Replicating Effective Programs framework, we will work with OCC to implement and measure the deployment, adoption and utilization of both teledermatology apps throughout all eligible VA sites. In one sub-aim, which is the principal focus of the current IRB application, we will conduct a formative evaluation of the implementation process at 3 early adopter sites to develop implementation strategies to guide subsequent nationwide deployment and research. Surveys and semi-structured interviews will assess Organizational Readiness for Change (ORC) at these sites regarding the apps, and link ORC to stages of implementation, barriers and facilitators to implementation, and implementation effectiveness as measured by uptake of the apps and actual use of teledermatology.

In the second sub-aim, we will also monitor deployment, adoption and utilization of both teledermatology apps nationally by analyzing remotely accessible data from the CDW and OCC. The primary data will be collected by CAPER under its own IRB approval, and aggregate data will be shared with the PIs and co-investigators. We will then correlate the degree of adoption with reach of the program (i.e., number of Veterans served) and stratify analyses of primary outcomes from Aim 1 based on degree of adoption.

At the conclusion of the project, we expect to document important indicators of mobile teledermatology’s effects on patient access in the nation’s largest healthcare system and to comprehensively understand the implementation of mobile teledermatology. These novel achievements will guide future mobile telemedicine endeavors in VA, and will inform other large healthcare organizations interested in telehealth.

8.3 DESIGN: Briefly describe the study design (e.g., observational, interventional, randomized, placebo-controlled, blinded, cross-over, cross-sectional, longitudinal, pharmacokinetic, etc.):

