VA Telederm is anticipated to be ready for national release in January 2017 and *My Telederm* in the spring of 2018, as part of VA’s Office of Connected Care operations. Beforehand, technical field testing will occur at San Francisco, Providence and Denver VHA facilities. For national rollout, each app will be targeted to sites that are clinically appropriate and best positioned to benefit from the app. Within these sites, the apps will be released in three month intervals according to allow a cross-sectional stepped-wedge cluster randomized trial for each app. We anticipate the affected population will represent VA’s as a whole.

The impact of teledermatology apps depends not only on their intrinsic effectiveness, but also on successful implementation and adoption by as many target sites and end-users as possible who then maintain the practice. Outcomes may be organized within the RE-AIM Framework, which encompasses multiple domains necessary for translating innovation into real-world practice. The Reach and Effectiveness domains are addressed in Aim 1; The Adoption, Implementation and Maintenance domains are the focus of Aim 2.

Aim 1 will assess each app’s effect on Veterans’ access to dermatology in a stepped-wedge cluster randomized trial. Corporate Data Warehouse (CDW) data pertaining to access will be collected remotely by the Center for Access Policy, Evaluation and REsearch (CAPER) under its own IRB approval. Multiple measures reflecting different aspects of access will be evaluated to achieve a comprehensive and accurate evaluation of each app’s impact. Aim 2 will focus on measuring the degree to which each app was implemented. Using semi-quantitative interviews and surveys of key VA staff members at the three early adopter sites (San Francisco, Denver and Providence VA Medical Centers) involved in technical testing as well as data in CDW and OCC databases, we will monitor implementation and identify organizational, individual, and app-specific factors that affect each app’s overall impact.

8.4 BACKGROUND AND SIGNIFICANCE: Briefly provide the background and significance of this study (e.g. why is this study needed) (space limit: one half page):

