8.5 PRELIMINARY STUDIES: Briefly summarize any preliminary studies relevant to your proposed research (space limit: one half page):

The proposed research is to assess the implementation and impact of mobile apps that are in the final stages of development, validation and checks for compliance with VA's privacy and safety requirements. In anticipation of the stepped-wedge cluster randomized trial, all VA facilities were examined for teledermatology activity relative to total dermatology activity.

The inclusion criterion for the first trial (*VA Telederm*) was that a site had a minimum of 0.1% and < 8.8% of its total FY2016 dermatology encounters under secondary stop codes 695/696 (teledermatology readings). VA

medical centers with no 695/696 activity in FY2016 or with zero full-time equivalent dermatologists were excluded since these sites likely lack the expertise, support and infrastructure to feasibly adopt teledermatology during the study period. In total, we identified 36 sites eligible for *VA Telederm*, teledermatology constituting between 0.1% and 8.8% of all dermatology encounters.

Conversely, the inclusion criterion for the second trial with *My Telederm* was that a site had $\geq 8.8\%$ of all FY2016 dermatology encounters under secondary stop codes 695/696. This indicated considerable pre-existing experience with consultative teledermatology and the likely presence of dermatology reader and support personnel needed to implement *My Telederm*. We identified 24 sites where teledermatology constituted 8.8% to 100% of total encounters.

In Aim 1, apps will be disseminated according to the stepped-wedge cluster randomization scheme determined by this research project, but otherwise is under the control of VA's Office of Connected Care as part of its operational plan to disseminate the apps to the clinical field. The main outcomes are measures that serve as proxies for access to dermatology services, and these are stored in VA's Corporate Data Warehouse (CDW) which is remotely accessible.

8.6 * TREATMENT PROTOCOL: Is this a treatment study, i.e. does this study intend to provide treatment to individuals with a medical or psychological condition: (REQUIRED)

Yes No

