 2. Using the semi-structured interview methods above, each core implementation team member, director of primary care, Chief of Dermatology, FTC, imager, and other staff members participating in processing or supporting teledermatology at each site will be interviewed. The sustainability interview will explore in more depth the areas surveyed in the PSI (Leadership, Collaboration, Demonstrating Program Results, Funding, and Program Responsivity). We have previously used the combination of PSI and qualitative interviews to evaluate the sustainability of a multi-facility program for the Office of Patient Centered Care and Cultural Transformation. This program sustainability interview guide will be introduced by the telephone consent script attached to this application.

Sub-Aim 2.2

Implementation of field sites will also be assessed at all participating sites by monitoring intermediate milestones and quantitative indicators of implementation that are available in CDW as well as from OCC's own telehealth database and Web and Mobile Solutions (WMS) device procurement program.

To understand how rapidly sites meet key milestones as a result of the OCC implementation process, and if the apps are more effective among sites that have reached more implementation milestones, randomized sites will be asked to complete a bi-monthly implementation site report monitoring key milestones, collected electronically via REDCAP on the VA intranet. This bi-monthly report is based on the bi-monthly site report utilized as part of the formative evaluation described above. Sites will be sent email reminders two weeks and one week prior to, and one week after the due date, with follow up via phone call, if necessary. Four of these randomized sites will be recruited to participate in semi-structured sustainability interviews using the same guides used in the formative evaluation and will be introduced by the telephone consent script attached to this application. These Interview data will be collected by

recording phone conversations directly onto secure VA networked servers or encrypted computers, using MS Teams and Phillips recorder.

8.11 INSTRUMENTS: List all questionnaires, surveys, interview, or focus group guides that will be used for this study:

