If the instruments are not complete or not available because they will be developed as part of this study, describe the basic content or include an outline and submit the final versions to the IRB with a modification for approval prior to use.

- 1) Site Information Report (revision attached)
- 2) Site Process Guide (attached)
- 3) Organizational Readiness for Change (ORC) Survey (revision attached)
- 4) Initial Interview Guide (attached)
- 5) Bi-Monthly Site Report (survey revision attached)
- 6) Follow-up Interview Guide (Allows participants to expand on the same areas covered by the bi-monthly site report)
- 7) Program Sustainability Index (survey revisions attached) Now VA T Program Sustainability index (attached) and My T Program Sustainability index (attached)
- 8) Sustainability Interview Guide (attached-Allows participants to expand on the same areas covered by the PSI survey)
- 9) Bi-Monthly Site Report for National Sites (attached)

Telephone/Email Consent Scripts for Contacting Subjects:

- 1) Email consent script (introduction and consent to ORC, both Bi-monthly reports, and Program Sustainability Index surveys)
- 2) Telephone consent script (introduction and consent to Site Process Guide, Initial Guide, Follow-up Guide, and Sustainability Guide)

Attach any unpublished instruments in the 'Other Study Documents' section of the Initial Review Submission Packet form after completing the study application. Published instruments should NOT be attached.

8.12 * BIOSPECIMEN COLLECTION: Are you drawing any blood or collecting other biosamples (e.g. tissue, buccal swabs, urine, saliva, hair, etc.) for analysis under this protocol and/or storage for future research: (REQUIRED)

Yes No

8.13 STATISTICAL METHODS: Briefly summarize the methods and types of analyses that will be performed:

Aim 1-Due to a lack of participation by sites during the study which was in part conducted during the novel coronavirus (COVID-19) pandemic, we were not able to follow the analysis plan for Aim 1 described below. Instead we focused on understanding factors associated with successful completion of consults with the mobile apps, examining differences between rural and urban Veteran users.

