In the third phase, we will apply the same criteria across the cases to determine if cross-case variation in implementation is consistent with the hypothesized relationships in the model. Consistent with the organization-level focus of the model, we will aggregate and analyze quantitative data on implementation policies and practices (e.g. staffing levels) and other study constructs using simple statistics. In addition, we will create within-case and between-case data displays that cross-tabulate the quantitative and qualitative data in order to facilitate the use of pattern-matching logic.

Sub-Aim 2.2: Collection of this data will be descriptively summarized to understand how rapidly sites meet key milestones as a result of the OCC implementation process, correlate the milestones to the number of patients serviced via the apps (i.e., reach), and allow for stratified analyses of main quantitative study results by degree of implementation based on reaching milestones to determine if the apps are more effective among sites that have reached more implementation milestones. We will analyze the qualitative data from the interviews in the same manner as described above for the formative evaluations using direct content analysis to examine themes within each case and to determine cross-case variation.

8.14 REFERENCES: List only the 5-10 most relevant references (a separate bibliography can be attached for reference purposes if this study involves novel approaches, agents, or an emerging technology that the IRB may not be familiar with):

1. Landow, S.M., D.H. Oh, and M.A. Weinstock, *Teledermatology within the Veterans Health Administration, 2002-2014*. *Telemed E Health*, 2015. **21**(10): p. 769-773.
2. Kilbourne, A.M., M.S. Neumann, H.A. Pincus, et al., *Implementing evidence-based interventions in health care: application of the replicating effective programs framework*. *Implement. Sci.*, 2007. **2**: p. 42.

3. Neumann, M.S. and E.D. Sogolow, *Replicating effective programs: HIV/AIDS prevention technology transfer*. AIDS Educ. Prev., 2000. **12**(5 Suppl.): p. 35-48.
4. Moullin, J.C., D. Sabater-Hernandez, F. Fernandez-Llimos, et al., *A systematic review of implementation frameworks of innovations in healthcare and resulting generic implementation*. Health Res. Policy Syst., 2015. **13**: p. 16.
5. Klein, K. and J. Sorra, *The challenge of innovation implementation*. Academy of. Management Review, 1996. **4**: p. 1055-1080.

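### Sub-Aim 2.2 relates milestones to patients served without accounting for time since release, and its stratified analysis still points to Aim 1 results whose plan was not followed

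*Combined protocol and SAP*

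**What the plan says.** Section 8.13 (Sub-Aim 2.2) describes a descriptive summary of how fast sites reach milestones. It will also "correlate the milestones to the number of patients serviced via the apps (i.e., reach), and allow for stratified analyses of main quantitative study results". The strata are to reflect how far implementation has progressed. Section 8.2 (Aim 2, second sub-aim) plans the same kind of correlation, between degree of adoption and the number of Veterans reached, and will "stratify analyses of primary outcomes from Aim 1 based on degree of adoption". Section 8.9 (Sub-Aim 2.2) gives the purpose as learning "if the apps are more effective among sites that have reached more implementation milestones", using two-monthly reports from the randomized sites. Section 10.1 puts the number of reporting site leads at 28.

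On timing, section 8.2 says "Both apps will be made available over a 2 year period in a randomized, stepped-wedge design", and section 8.3 says "the apps will be released in three month intervals". Section 8.5 says "apps will be disseminated according to the stepped-wedge cluster randomization scheme determined by this research project". Section 8.13 gives a trial duration of 2.5 years.

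On Aim 1, section 8.13 opens with a notice that "we were not able to follow the analysis plan for Aim 1 described below", because too few sites took part, and continues: "Instead we focused on understanding factors associated with successful completion of consults with the mobile apps", with a rural-urban comparison.

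**The concern.** A site released in the first step has had longer than a site released in the last step both to reach milestones and to serve patients. If the two totals are compared at one calendar date, early sites tend to be high on both and late sites low on both, even when neither influences the other. No section sets a time origin, a common window, an offset or an adjustment for time since release. A reader could then take an effect of release date as evidence that implementation milestones drive reach.

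The stratified analysis has a different problem. It is meant to show whether the apps work better at sites further along in implementation, but the effect estimates it would stratify belong to an analysis plan that was not followed. A reader cannot tell what this analysis now consists of.

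**Working it through.** The plan states no correlation, threshold or sample-size figure for Sub-Aim 2.2, so there is nothing to reproduce. The check asks how large an association release timing alone can create.

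**From the documents.** 28 reporting sites (10.1); three-month steps (8.3) over two years (8.2); 2.5-year duration (8.13). The number of steps is not stated. 24 / 3 = 8 is inferred, with releases at months 0 to 21. Time since release is then 3 to 24 months at a 24-month cut-off and 9 to 30 months at a 30-month cut-off, a spread of 21 months either way.

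**Assumed.** On average 1 milestone and 20 patients per site-quarter. Site rates come from independent gamma distributions with between-site coefficient of variation (CV) 0.25, 0.5 or 1.0, and counts are Poisson. All 28 sites follow one schedule. The true link is zero.

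**Unadjusted Spearman correlation of totals, mean over 5,000 runs:**

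| Scenario | Cut-off | CV 0.25 | CV 0.5 | CV 1.0 |
|---|---|---|---|---|
| 8 steps | 24 months | 0.67 | 0.48 | 0.22 |
| 8 steps | 30 months | 0.51 | 0.29 | 0.09 |
| 8 steps, half of sites never use the app | 24 months | 0.18 | 0.13 | 0.06 |
| 8 steps, half of sites never use the app | 30 months | 0.13 | 0.08 | 0.03 |
| Stagger compressed to 9 months | 24 months | 0.19 | 0.08 | 0.02 |
| Stagger compressed to 9 months | 30 months | 0.13 | 0.05 | 0.01 |
| Simultaneous release | either | 0 | 0 | 0 |

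At CV 0.5 with 8 steps, the 10th to 90th percentile is 0.30 to 0.66 at 24 months and 0.07 to 0.51 at 30 months. With a finite list (8 milestones at 2 per quarter, and patient volume rising over 12 months) the means are 0.75 / 0.60 / 0.31 at 24 months and 0.50 / 0.34 / 0.12 at 30 months. A second set of assumed rates (0.5 milestones and 3 patients per month) gives the same pattern at 30 months: 0.71 with identical sites, 0.37 with moderate and 0.16 with large site variation, and 0.00 with simultaneous release.

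**Adjustment.** Let M be the rank of milestones, P the rank of patients served and T the rank of months since release. The partial rank correlation is

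r(MP·T) = [r(MP) − r(MT) r(PT)] / √{[1 − r(MT)²][1 − r(PT)²]}.

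With no true link, r(MP) is close to r(MT) r(PT), so the numerator is close to zero. The simulated mean is 0.01 to 0.02 where rates are stable over calendar time, at most 0.04 with the slowdown described next, and about 0.06 or below in every case run. All 28 sites stay in.

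**A fixed window after release.** With rates stable over calendar time, counting both quantities over the same 3 to 12 months after release also gives means within 0.01 of zero. That does not survive a calendar effect, and section 8.13 places part of the study in the pandemic. Suppose both rates fall to 30% in quarters 5 to 7. At a 30-month cut-off a 6-month window then gives 0.38 / 0.29 / 0.12, against 0.41 / 0.23 / 0.08 for the unadjusted totals, so it is no better at CV 0.5 and 1.0. The partial correlation copes because, at a common cut-off, months since release and release date carry the same information.

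A window also drops sites. With 4 sites at each of the four shortest exposures, a 6-month window at 24 months keeps 28 − 4 = 24, and a 12-month window keeps 28 − 12 = 16. At 30 months they keep 28 and 24.

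**The stratified analysis.** No arithmetic applies. Section 8.2 stratifies Aim 1 primary outcomes. Sections 8.9 and 8.13 ask whether the apps are more effective at sites with more milestones. The Aim 1 notice replaces the planned comparison with factors associated with completed app consults. As described, that has no comparison with sites lacking the app, so it yields no app effect that could be larger in one stratum than in another.

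**The case against.** The sentence in section 8.13 begins with how rapidly milestones are met, so the milestone measure might be a speed rather than a total. Section 11.14 has site reports running for two years; if that ran from each site's own start, milestone follow-up would already be equal. The field asks for a brief summary, the analysis is descriptive, and no test is planned. The collecting centre's own plan may define a window. Poor participation may mean the stagger never ran as planned. The simulation puts both apps on one schedule, and every rate in it is assumed.

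Much of this stands as a limit on size. It does not supply the missing rule. Speed is listed as a separate item, with no origin, and is not carried into the correlation. The two years of reports have no stated start, and patients served would still be a raw count. The time fixed effects in section 8.13 belong to the Aim 1 mixed model.

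On the second part, the phrase about main quantitative results could cover the replacement analysis, and the superseded Aim 1 text is kept openly. But section 8.2 names Aim 1 primary outcomes, and the effectiveness question in 8.9 and 8.13 needs an effect that the replacement does not describe.

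A reader might infer that any reported correlation is an artefact, or is inflated by 0.5 or more. The documents do not support that: they do not show that the stagger occurred, and the illustrative range reaches zero.

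**Conclusion.** The concern holds, as a minor one. Followed as written, the milestone-reach correlation can be positive through time since release alone. The mean Spearman value runs from about 0 with little or no stagger to about 0.5 to 0.7 with full stagger and similar sites, and is lower when sites differ widely, many never use the app, or the cut-off is later. These sizes rest on assumed rates, an inferred eight steps and a single schedule, so they show what is possible and do not estimate the bias in this study. A reader might also infer that a fixed post-release window is a sufficient cure; given the pandemic, it is not.

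The second part rests on the text alone: sections 8.2, 8.9 and the Sub-Aim 2.2 part of 8.13 do not agree with the Aim 1 notice in 8.13. This is a matter of reconciling the text, and no size attaches to it.

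**What to change.** In section 8.13 (Sub-Aim 2.2) and section 8.2, analyse each app separately. Report the milestone-reach correlation as a partial rank correlation adjusted for months since each site's own release, keeping all sites, and label it descriptive and non-randomised. A count of both quantities over the same fixed window after release may be added as a sensitivity analysis, with a note that it drops late-released sites and is not protected against calendar-time effects. A simple rate per quarter is not a safe substitute: it is close to unbiased in the base case, but in the finite-list case it gives −0.31 / −0.19 / −0.06 at 24 months and −0.44 / −0.22 / −0.06 at 30 months.

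Reconcile sections 8.2, 8.9 and 8.13 with the Aim 1 notice. Either withdraw the stratified effectiveness analysis, or name the results it now uses, define strata by milestones relative to time since release, and drop the claim that it shows whether the apps are more effective.

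The cost is wording, one degree of freedom and the actual release dates, which depend on the Office of Connected Care. Separate analyses are less precise, and section 10.1 does not say how the 28 sites divide between the apps. No new data collection from sites is needed.
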